8.2.1.5. All GS-9883/F/TAF Analysis Set

All GS-9883/F/TAF analysis set will include all subjects who (1) are randomized into the study and (2) have received at least 1 dose of the blinded GS-9883/F/TAF or OL GS-9883/F/TAF. Subjects will be grouped into two groups: (1) All GS-9883/F/TAF group, including all subjects who randomized into GS-9883/F/TAF and received at least 1 dose of GS-9883/F/TAF; (2) DTG + F/TAF to GS-9883/F/TAF group, including all subjects who randomized to DTG + FTAF in the double-blinded phase and received at least 1 dose of OL GS-9883/F/TAF in the extension phase. This is the primary analysis set for the all GS-9883/F/TAF efficacy and safety analyses.

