3. GENERAL CONSIDERATIONS FOR DATA ANALYSES

The Final Analysis will include two sets of analysis: randomized phase analysis and all B/F/TAF analysis. All table summaries in this final analysis will be based on data included in the All B/F/TAF analysis (eg, data collected during the study period when participants were on B/F/TAF). Randomized phase analysis (eg, including data collected during double-blind phase when participants were on the double-blind study drug) and the corresponding analysis window defined in Section 3.8, will be used to support applicable listings where data collected from the double-blind phase are indicated. The wording of randomized phase or double-blind phase might be used interchangeably throughout the SAP and in the TFLs.

Randomized Phase Analysis:

- For subjects who are never treated in the extension phase of the study including those who prematurely discontinue the randomized study drug or who complete the randomized study drug and do not receive any dose of B/F/TAF in the extension phase, all available data will be included in the randomized phase analysis.
- For subjects who complete the randomized phase and receive at least 1 dose of B/F/TAF in the extension phase, the randomized phase analysis will include (1) all available AE, concomitant medication, pregnancy, and death data collected prior to the extension phase first dose date; (2) all available other data, such as laboratory, vital sign, electrocardiogram (ECG), collected on or prior to the extension phase first dose date.

All B/F/TAF Analysis:

- For subjects who receive B/F/TAF in the randomized phase, all available data for subjects who actually receive B/F/TAF in the randomized phase will be included.
- For subjects who actually receive DTG+F/TAF in the randomized phase and receive at least 1 dose of B/F/TAF in the extension phase, (1) all available AE, concomitant medication, pregnancy, and death data with start date **on or after** the first dose date of B/F/TAF in the extension phase and (2) all available other data, such as laboratory, vital sign, and ECG data, collected **after** the first dose date of B/F/TAF in the extension phase will be included. The data collected **on or prior to** the first dose date of B/F/TAF will be used to derive the baseline value for the all B/F/TAF analysis.

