Note that all data for subjects who actually receive DTG+F/TAF in the randomized phase and do not receive any dose of B/F/TAF in the extension phase will be excluded from all B/F/TAF analysis. The actual treatment received will differ from the randomized treatment only when the actual treatment received differs from randomized treatment for the entire treatment duration.

Analysis results will be presented using descriptive statistics. For categorical variables, the number and percentage of subjects in each category will be presented; for continuous variables, the number of subjects (n), mean, standard deviation (SD) or standard error (SE), median, first quartile (Q1), third quartile (Q3), minimum, and maximum will be presented.

All statistical tests will be 2-sided and performed at the 5% significance level unless otherwise specified.

For All B/F/TAF analysis, no statistical comparison between treatment groups will be conducted.

By-subject listings will be presented for all subjects in the All Randomized Analysis Set unless otherwise specified, and sorted by subject ID number, visit date, and time (if applicable). Data collected on log forms, such as AEs, will be presented in chronological order within a subject. The treatment group to which subjects were randomized will be used in the listings. Most listings will be provided for all randomized analysis set for data from both phases of the study. Some listings for All B/F/TAF analysis set will also be provided.

In general, age (in years) on the date of the first dose of study drug will be used for analyses and presentation in listings. For randomized but never dosed subjects, age on the date of randomization will be used. For screen failures, age on the date of the informed consent was signed will be used. If only birth year is collected on the eCRF, “01 January” will be used for the unknown birth day and month for the purpose of age calculation, similarly, if only birth year and month are collected on the eCRF, “01” will be used for the unknown birth day for the purpose of age calculation.

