3.2. Subject Grouping

For analysis using the All Randomized Analysis Set, subjects will be grouped by the randomized treatment (labeled as B/F/TAF vs. DTG/F/TAF).

For all analyses included in the all B/F/TAF analysis, subjects will be grouped into the following 2 groups:

- B/F/TAF group: This group includes all subjects who actually received B/F/TAF in the randomized phase of this study, regardless whether subjects receive any B/F/TAF in the extension phase or not.
- DTG/F/TAF to B/F/TAF group: This group includes all subjects who actually received DTG+F/TAF regimen in the randomized phase of this study and then receive at least 1 dose of B/F/TAF in the extension phase.

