- 7) Randomized treatment (ie, TRT01P in ADSL) are derived from IXRSRAND, while actual treatment received (ie, TRT01A in ADSL) is assigned as the randomized treatment if subject took at least 1 dose of study drug and assigned as blank if subject never dosed.
- 8) Enrollment by Stratum: using actual HIV-1 RNA or CD4+ cell count screening value, the last screening value (with visitnum < 0) prior to randomization date and time.
- 9) In disposition table, the reasons for premature discontinuation are displayed in the order as they appear on the eCRF.

10) Body mass index (BMI) and Body Surface Area (BSA)

BMI and BSA will be calculated only at baseline as follows:

- $BMI = (\text{weight [kg]} / (\text{height [meters]}^2))$
- $BSA (m^2) = \text{SQRT}([\text{Height(cm)} \times \text{Weight(kg)}] / 3600)$

Baseline height and weight will be used for this calculation.

- 11) Please note, “Not Permitted”, “Unknown”, or missing categories will be excluded for percentage calculation and also excluded for p value generation for categorical data analysis (eg, CMH test or Fisher exact test). Except for Mode of infection (HIV Risk Factors), where “Unknown” will be included for percentage calculation, since a subject may fit more than 1 HIV risk factors, therefore percentage may add to more than 100% and no p-value will be generated.

Subjects with Race = “Not Permitted” will also be excluded to define Race subgroup (ie, black vs. nonblack) for efficacy subgroup analysis.

12) Last Dose Date and Last Study Date

- a) Last Dose Date (ie, TR01EDT or TR01EDTC for randomized phase last dose date, and TR02EDT or TR02EDTC for extension phase last dose date) in ADSL.

Randomized Phase Last Dose Date:

For **B/F/TAF** or **DTG/F/TAF** subjects with a partial last dosing date (ie, month and year of last dose are known), the minimum of {(extension phase first dose date – 1 day, if available), (the latest of the dispensing dates of study drug bottles, study drug start dates and end dates (based on EX dataset with study drug in randomized phase), and the imputed last dose date [day imputed as 15])} will be used as the final imputed last dose date. However, if dispensing date’s month is after last dose date’s month, data query is needed. If subject died and the death date is complete (ie, not partial date) and before the imputed last dose date, the complete death date should be used as the imputed last dose date.

Extension Phase Last Dose Date:

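### SAP Appendix 6 item 7 sets actual treatment equal to randomized treatment for every dosed subject, contradicting the SAP's own rule for subjects on the wrong regimen throughout

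*SAP*

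**What the plan says.** SAP Section 3 states that actual and randomized treatment will differ "only when the actual treatment received differs from randomized treatment for the entire treatment duration". The All B/F/TAF analysis is built on that notion of actual treatment:

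- Data inclusion (Section 3): "all available data for subjects who actually receive B/F/TAF in the randomized phase will be included".
- First group (Section 3.2): "This group includes all subjects who actually received B/F/TAF in the randomized phase of this study".
- Second group (Section 3.2): "This group includes all subjects who actually received DTG+F/TAF regimen in the randomized phase of this study", with the further condition of at least one B/F/TAF dose in the extension.
- Study Day 1 (Section 3.8.1), and through it baseline and analysis windows, is split by the same two groups.

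Appendix 6 item 5 groups the Safety Analysis Set by treatment actually received, and item 6 groups the FAS as randomized. Item 7 then gives the derivations. For the planned arm: "Randomized treatment (ie, TRT01P in ADSL) are derived from IXRSRAND". The actual arm, TRT01A, "is assigned as the randomized treatment if subject took at least 1 dose of study drug", and is blank if the subject was never dosed.

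Protocol 8.2.1.5 defines the first group of the same analysis differently, "including all subjects who randomized into GS-9883/F/TAF" with at least one dose of that product. Its second group is likewise defined by randomized arm plus at least one open-label dose. SAP Sections 6.4 and 7.7 report no change from the protocol-specified analyses.

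**The concern.** A programmer following item 7 produces an actual-treatment variable that equals the randomized arm for every dosed subject. The body of the SAP says the two can differ. The distinction that items 5 and 6 draw between the Safety Analysis Set and the FAS would also vanish by construction.

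The final analysis reports all its summary tables on All B/F/TAF data. A subject whose blinded regimen was wrong from start to finish is the one kind of subject for whom grouping by actual treatment matters, and item 7 would classify that subject by the regimen not taken. Exposure, adverse events, laboratory shifts and virologic response would then sit in the wrong group, or be missing from the tables.

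**Working it through.** No figure in the plan needs reproducing. The check applies each rule to each combination of randomized arm and regimen taken for the whole randomized phase, assuming that the groups are programmed from TRT01A.

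Where the subject took the assigned regimen, TRT01A is the randomized arm and agrees with Section 3. The rules part in the other cases:

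| Randomized to | Took throughout | Treated in extension | SAP 3, 3.2, 3.8.1 | Item 7 | Protocol 8.2.1.5 |
|---|---|---|---|---|---|
| B/F/TAF | DTG+F/TAF | No | Not in analysis | B/F/TAF group, Day 1 at first randomized-phase dose | Not in set (no B/F/TAF dose) |
| B/F/TAF | DTG+F/TAF | Yes | DTG to B/F/TAF group, Day 1 at first extension dose | B/F/TAF group, Day 1 at first randomized-phase dose | First group (by randomization) |
| DTG+F/TAF | B/F/TAF | No | B/F/TAF group, Day 1 at first randomized-phase dose | Not in analysis | In the set, but in neither group |
| DTG+F/TAF | B/F/TAF | Yes | B/F/TAF group, Day 1 at first randomized-phase dose | DTG to B/F/TAF group, Day 1 at first extension dose | Second group (by randomization) |

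Item 7 disagrees with the body of the SAP in all four rows. Its group placement matches the protocol in the two extension rows but not in the first row, so it does not simply implement the protocol either.

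**Size per subject.** With the planned 300 per arm, one subject is 1/300 = 0.33 percentage points of a group's denominator, and more if the group is smaller.

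**Size of the date error.** It arises only in the two rows with extension treatment. The blinded phase lasts at least 144 weeks, or 144 × 7 = 1,008 days, before the first extension dose. Study Day 1 would be too early by about that much or more in the second row, and too late by the same amount in the fourth. In the fourth row the blinded-phase B/F/TAF data would also drop out. In the two rows without extension treatment the error is wrongful inclusion or exclusion, with no shift of this kind.

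**The case against.** **Item 7 can be read compatibly.** Items 5 and 6 speak of a dose of the randomized study drug. If item 7 means the same, and that phrase means the subject's own assigned regimen, it says only that anyone who took a dose of that regimen is analysed as randomized, which is Section 3 seen from the other side. This does not hold. Item 7's only other branch is blank for subjects never dosed, and Section 3 defines study drug in the randomized phase as either regimen. Even on the kinder reading, a subject on the wrong regimen throughout would fall in neither branch, and the same line would have to be written.

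**The reach of TRT01A is inferred.** This stands. TRT01A appears only in item 7. SAP 3.1.2 defines the set by receipt of a B/F/TAF dose, and 3.8.1 takes dose dates from the Study Drug Administration eCRF. A reader might infer that Study Day 1, baseline, adverse event dating and grouping are all driven by TRT01A. The SAP does not say so. It only gives TRT01A the label that those sections use.

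**The wrong-drug listing is weak evidence.** This also stands. SAP 4.3 plans a listing of subjects who received the wrong study drug, and a reader might take it as a sign that whole-duration cases are expected. It covers any such event, including one wrong bottle at one visit, and those subjects stay in their randomized arm under both rules. Bottles are assigned through the IWRS at each visit, so an error lasting throughout is most plausible in an early discontinuer, for whom no 144-week shift arises.

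**The affected outputs are descriptive.** Correct. No comparison between groups is made in the All B/F/TAF analysis.

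**Conclusion.** Item 7 is wrong as written. It contradicts Section 3 and the actual-treatment wording in Sections 3.2 and 3.8.1 and in Appendix 6 item 5, and nothing elsewhere in the SAP overrides it. What it disables is only the actual-versus-randomized distinction in the randomized phase. The dosed/never-dosed split and the extension-dose requirement still work.

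The practical effect rests on two conditions that the documents do not settle: that the All B/F/TAF groups are programmed from TRT01A, and that at least one subject took the wrong regimen for the entire randomized phase. If both hold, the error is confined to those subjects. If there are none, no number changes. It would go too far to say that every misallocated subject gets a Study Day 1 wrong by 144 weeks, because that needs treatment in the extension as well.

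The primary Week 48 analysis is not touched: the FAS is grouped as randomized, and that analysis was done under an earlier SAP.

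The mismatch between SAP 3.2 and protocol 8.2.1.5 exists whether or not anyone was misallocated, and the SAP's statements of no change from protocol pass over it.

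**What to change.** Amend item 7 so that TRT01A is the other regimen when dispensing and kit records show that it was taken for the entire randomized phase, the randomized arm for all other dosed subjects, and blank if never dosed. State in the same place that the Section 3.2 groups are derived from TRT01A, if that is the intention.

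Reconcile SAP 3.2 with protocol 8.2.1.5. Either keep grouping by treatment actually received and record the difference from the protocol in SAP 6.4 and 7.7, or align 3.2 with the protocol's grouping by randomized arm plus at least one dose. If the second is chosen, the Section 3 sentence must change too, and the protocol's gap in the third row of the table needs a rule.

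The cost is one line of specification and a short note. The IWRS assigns bottle numbers at each visit (protocol 5.1), and accountability records hold the kit number dispensed (protocol 5.5). Because the SAP is already signed, its Section 1 gives the route: document the change in the CSR. If the wrong-drug listing shows no whole-duration case, a sentence in the CSR saying so removes any doubt about the results.

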6.6. Post-treatment Assessments

6.6.1. Early Study Drugs Discontinuation Assessments

If the subject discontinues study drug prior to the End of Blinded Treatment Visit, the subject will be asked to return to the clinic within 72 hours of stopping study drugs for the Early Study Drugs Discontinuation Visit. The subject will be asked to continue attending the scheduled study visits through the End of Blinded Treatment Visit.

If the subject discontinues study drug during the Open Label rollover extension, the subject will be asked to return to the clinic within 72 hours of stopping the study drug for the Early Study Drugs Discontinuation Visit.

At the Early Study Drugs Discontinuation Visit, any evaluations showing abnormal results indicating that there is a possible or probable causal relationship with the study drug, will be repeated weekly (or as often as deemed prudent by the Investigator) until the abnormality is resolved, returns to Baseline, or is otherwise explained.

The following evaluations are to be completed at the Early Study Drugs Discontinuation Visit:

- Review of AEs and changes in concomitant medications
- Complete physical examination (urogenital/anorectal exams will be performed at the discretion of the Investigator)
- 12-lead ECG performed supine (blinded treatment phase only)
- Vital signs measurement (blood pressure, pulse, respiration rate, and temperature), including weight
- Urine collection for the following laboratory procedures:
 - Urinalysis
 - Urine pregnancy test (females of childbearing potential only); positive urine pregnancy tests will be confirmed with a serum test
- CCU
- Blood sample collection for the following laboratory analyses:
 - Chemistry profile: alkaline phosphatase, AST, ALT, GGT, total bilirubin, direct and indirect bilirubin, total protein, albumin, LDH, CPK, bicarbonate, BUN, calcium, chloride, creatinine, glucose, phosphorus, magnesium, potassium, sodium, uric acid, and amylase (reflex lipase testing is performed in subjects with total amylase > 1.5 × ULN), and TSH

- Estimated glomerular filtration rate according to the Cockcroft-Gault formula
- Hematology profile: complete blood count (CBC) with differential and platelet count
- Plasma HIV-1 RNA
- CD4+ cell count
- Plasma storage sample for safety, virology, or PK testing
- Plasma HBV DNA (for subjects who meet the definition of HBV infection anytime)
- HIV-1 genotype/phenotype testing for subjects with virologic failure
- Drug accountability

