3.8. Analysis Windows

3.8.1. Definition of Study Day

Study Day 1 for the Randomized Phase analysis is defined as the day when the first dose of study drug (ie, B/F/TAF, DTG /F/TAF) was taken, as recorded on “Randomized Phase” the Study Drug Administration eCRF form.

Last Dose Date for the Randomized Phase analysis is the latest of the randomized study drug (including B/F/TAF or DTG/F/TAF) end dates recorded on the Study Drug Administration eCRF form.

If last dose date for the Randomized Phase analysis is missing (eg, only year of last dose date is known or completely missing due to lost to follow-up), the latest of the randomized study drug start dates and end dates or the latest clinical and laboratory visit dates prior to the first dose date of B/F/TAF in the extension phase (if applicable), excluding the 30-day follow-up visit date, will be used to impute the last dose date. For other partial missing last dose date, please see the programming specifications for imputation rule details.

Study Day 1 for the all B/F/TAF analysis is defined as

- For subjects who actually received B/F/TAF in the randomized phase of this study (ie, B/F/TAF group), Study Day 1 for the all B/F/TAF analysis is defined as the day when the first dose of B/F/TAF in the randomized phase was taken, as recorded on the Study Drug Administration eCRF form.
- For subjects who actually received DTG/F/TAF in the randomized phase of this study and then receive at least 1 dose of B/F/TAF in the extension phase (ie, DTG/F/TAF to B/F/TAF group), Study Day 1 for the all B/F/TAF analysis is defined as the day when the first dose of B/F/TAF in the extension phase was taken, as recorded on the Study Drug Administration eCRF form.

Last Dose Date for the All B/F/TAF Analysis is the latest of B/F/TAF (including both phases) end dates recorded on the Study Drug Administration eCRF form.

If the last dose date for the all B/F/TAF analysis is missing (eg, only year of last dose date is known or completely missing due to lost to follow-up), the latest of the B/F/TAF (including both phases) start dates and end dates, the latest clinical and laboratory visit dates, excluding the 30-day follow-up visit date, will be used to impute the last dose date.

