For subjects with a partial last dosing date (ie, month and year of last dose are known), the minimum of { (the latest of the dispensing dates of study drug bottles, study drug start dates and end dates (based on EX dataset with study drug in extension phase), and the imputed last dose date [day imputed as 15])} will be used as the final imputed last dose date. However, if dispensing date's month is after last dose date's month, data query is needed. If subject died and the death date is complete (ie, not partial date) and before the imputed last study date, the complete death date should be used as the imputed last study date.

- b) Last Study Date is the latest of the randomized or extension phase (if available) study drug start dates and end dates, the clinic visit dates, and the laboratory visit dates, including the 30-day follow-up visit date. If study drug start dates or end dates is partially missing (ie, only year and month are known), the day will be imputed as 15 for the purpose of this analysis.

If subject died and the death date is complete (ie, not partial date) and before the imputed last study date, the complete death date should be used as the imputed last study date.

13) Toxicity Grades:

Two type of treatment emergent lab abnormalities flag variables will be derived for laboratory data as applicable. For treatment emergent flag used in listing for randomized analysis set, the baseline toxicity grade will be based on baseline value defined as the last nonmissing value obtained on or prior to the first dose of randomized study drug. For treatment emergent flag used for the All B/F/TAF analysis summary and listing using all B/F/TAF analysis set, the baseline toxicity grade will be based on baseline value defined as the last nonmissing value obtained on or prior to the first dose of B/F/TAF.

Treatment-emergent laboratory abnormalities will be summarized for all B/F/TAF analysis, following the same rules bellow.

- a) For toxicity grade summaries, include all post-baseline graded results up to 30 days after the last dose of study drug B/F/TAF, not just those used in by-visit summaries.

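### Last dose date: the extension-phase death cap names the wrong date, and a missing date can be filled with a visit made after drug was stopped (wrong as written, low impact)

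*SAP*

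**What the plan says.** **Partial date (month and year known), SAP Appendix 6 item 12a.** Both phases take the latest of the dispensing dates, the drug start and end dates, and a date with the day set to 15. The extension rule ends "and the imputed last dose date [day imputed as 15])} will be used as the final imputed last dose date". Each phase then has a sentence for subjects with a complete death date:

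- Randomized phase: if death is "before the imputed last dose date, the complete death date should be used as the imputed last dose date".
- Extension phase: if death is "before the imputed last study date, the complete death date should be used as the imputed last study date".

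The extension sentence appears again in item 12b, which defines the last study date and where it is correct.

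**Year only, or nothing known, SAP 3.8.1.** For the All B/F/TAF analysis, the latest of the B/F/TAF start and end dates and "the latest clinical and laboratory visit dates, excluding the 30-day follow-up visit date, will be used to impute the last dose date". The randomized-phase rule is the same but limited to visits before the first extension dose, where there is one. The SAP's example of a completely missing date is loss to follow-up.

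**Visits after stopping drug, Protocol 6.6.1.** For a subject who stops in the blinded phase: "The subject will be asked to continue attending the scheduled study visits through the End of Blinded Treatment Visit". Protocol 6.4 says the scheduled evaluations are made whether or not the subject is still on study drug. Protocol 6.6.2 waives the 30-day follow-up visit for a blinded-phase discontinuer who attends at least one visit after the discontinuation visit.

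**The concern.** The two item 12a rules are parallel, and only the randomized-phase rule limits the last dose date at death. No other text limits the extension-phase last dose date in this way. A program that follows the text would leave the last dose after death. It could also leave the last dose date later than the last study date, since that date is the one being capped.

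In 3.8.1, excluding the 30-day follow-up visit shows that a post-treatment visit is not meant to stand in for the last dose. But a blinded-phase discontinuer who stays in the study normally has no 30-day visit, and has instead a series of off-drug visits that the rule does not exclude. Nor does the rule respect a year of last dose that is known.

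The date feeds exposure and Kaplan-Meier time to discontinuation (SAP 4.2.1), the 1-day on-treatment cut for CD4 (6.3.2.2), the 30-day windows for adverse events, deaths and laboratory abnormalities (7.1.5.1, 7.1.6, 7.2.2), and concomitant medication (7.4.2). The two faults do not reach all of these equally.

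**Working it through.** The plan states no figure to reproduce. The check applies the written rules to dates.

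**1. Extension-phase death limit**

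Inputs: day imputed as 15 (item 12a); death on day d of the same month as the last dose; last dispensing in an earlier month.

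Days after death = 15 − d, for d = 1 to 14. This gives 14 days at d = 1 and 1 day at d = 14. For d of 15 or later there is no overrun. A dispensing date later than the 15th cannot create one, because drug is not dispensed after death.

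Example: last drug 3 June 2020, death 5 June 2020, only June 2020 recorded.

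- Extension wording: 15 June, which is 15 − 5 = 10 days after death.
- Randomized-phase wording: 5 June, so 0 days after death.

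All pairs of a last-dose day and a same or later death day, in months of 31, 30 and 28 days:

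- Pairs: 496 + 465 + 406 = 1,367.
- Imputed date after death: 105 per month × 3 = 315.
- Largest overrun: 14 days.
- Pairs in which the treatment-emergent status of the death changed: 0.

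These are counts of calendar combinations, not probabilities. Adverse events, laboratory values and CD4 samples cannot change class either: none can post-date death, so whatever falls inside the window with the 15th also falls inside it with the death date.

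**2. Missing or year-only date**

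Inputs: true stop at week s; visits attended to Week 144; no stop month known.

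Overshoot = 144 − s weeks, and days = 7 × (144 − s).

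| True stop | Overshoot (weeks) | Days | Years (days ÷ 365.25) |
|---|---|---|---|
| Week 4 | 140 | 980 | 2.7 |
| Week 12 | 132 | 924 | 2.5 |
| Week 24 | 120 | 840 | 2.3 |
| Week 48 | 96 | 672 | 1.8 |
| Week 96 | 48 | 336 | 0.9 |

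Attending visits after Week 144 adds to these.

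Known-year example, with an assumed Day 1 of 1 March 2016: a stop at Week 12 (Day 84) is 23 May 2016. If only 2016 is recorded, the rule gives the Week 144 visit (Day 1008), 3 December 2018. That is 1008 − 84 = 924 days late and two calendar years past the recorded year.

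With the fix below, a year cap alone limits the date to 31 December 2016, 222 days late. Using visits only up to the discontinuation visit, which Protocol 6.6.1 asks for within 72 hours of stopping, reduces the error to about 3 days if that visit was held on time.

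**3. Who can be affected in the tables**

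- B/F/TAF subjects who stopped blinded drug and kept attending: yes.
- DTG + F/TAF subjects who stopped blinded drug: no. They cannot enter the extension (Protocol 6.5.2) and are excluded from the All B/F/TAF analysis (SAP 3).
- Subjects who stopped in the extension: hardly, because their scheduled visits end when drug is stopped (Protocol 6.6.2).

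**The case against.** The item 12a slip is easy to recognize. The heading, the parallel randomized-phase rule and the same sentence in 12b all show what was meant, and a careful programmer might correct it silently. That bears on how likely the error is to reach the output, not on whether the text is right.

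The 3.8.1 case needs an unlikely subject: one who stopped blinded drug, attended for months or years afterwards, and for whom nobody could establish even the month of stopping. The protocol works against this, with a discontinuation visit within 72 hours that includes drug accountability (6.6.1), drug start and end dates required in source records (9.1.5), and source verification with queries (9.1.6). If the month is known, item 12a applies and uses no visit dates. For true loss to follow-up, visits stop too and the latest visit is a sensible substitute. All of this stands, and it makes the long overrun a rare worst case.

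The analyses concerned are also modest. Adverse events are reported as numbers and percentages of subjects, so a late date can only add events to B/F/TAF. In the Kaplan-Meier analysis the discontinuation still counts, only later.

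Two stronger readings are tempting, and the documents support neither. A reader might infer that the death slip turns off-drug events into on-drug ones; the check above shows that it cannot. A reader might also infer years of false exposure as a typical effect, or a threat to the comparison of the two regimens. The documents give no count of missing dates, this SAP makes no between-group comparison, and the Week 48, 96 and 144 endpoint analyses were completed under separate plans (SAP 6, 6.1 and 6.2.1).

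**Conclusion.** Both rules are wrong as written, and the impact is low.

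- **Item 12a:** 1 to 14 days past death, only for a subject who died in the first 14 days of the month of last extension dose, with a complete death date and an unknown dose day. It lengthens exposure and Kaplan-Meier time and changes no adverse event, laboratory, CD4 or treatment-emergent-death classification.
- **Section 3.8.1:** at worst about 2 to 3 years, only for a B/F/TAF subject who stopped drug in the blinded phase, kept attending, and has at most the year of last dose recorded. For such a subject, exposure and time to discontinuation are overstated, and off-drug events, laboratory values and CD4 counts enter the on-treatment summaries.

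This assumes that the rules are programmed literally and, for the table above, that visits are attended to Week 144. The number of subjects affected is expected to be very small but cannot be computed from the documents.

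**What to change.** 1. **SAP Appendix 6, item 12a, extension phase.** In the death sentence, replace the last study date with the last dose date in both places, to match the randomized-phase rule. Leave item 12b unchanged.
2. **SAP 3.8.1, missing or year-only date.** Keep the exclusion of the 30-day follow-up visit and, in the randomized-phase rule, the limit to visits before the first extension dose. Add:
   - For subjects recorded as having prematurely discontinued study drug, use only visits on or before the Early Study Drugs Discontinuation Visit or, if it was not done, the discontinuation recorded on the Study Drug Completion form.
   - The imputed date may not exceed 31 December of a known year of last dose.

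Subjects truly lost to follow-up keep the present visit-based rule, subject to the same year cap. No separate death limit is needed in 3.8.1, because visits cannot follow death.

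Cost: two lines of specification, using data already collected. SAP Section 1 provides for changes after finalization to be documented in the clinical study report.
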